## **6.2 Exclusion Criteria:**

- Diabetes (pre-existing or gestational)\*
- Major fetal abnormality
- Prior corticosteroid use in this pregnancy (intramuscular corticosteroid use for fetal lung maturity)
- Prior enrolment in the C\*STEROID Feasibility Study or C\*STEROID Trial, in a previous pregnancy

\*Women with pre-existing or gestational diabetes will not be included in this trial as risks for neonatal respiratory morbidity and hypoglycaemia are significantly different in these populations. Corticosteroid use may also significantly disrupt glycaemic control in women with diabetes, with potential to ‘unblind’ treatment allocation and pose risk to these women. The effect of corticosteroids prior to planned CS in women with diabetes will be examined in other studies.

## **6.3 Withdrawal of Participants**

All study participants are free to discontinue the study drug and/or withdraw their consent at any point during treatment without prejudice. Participants who elect to discontinue the study drug early (receive no or one dose only) will continue with all other trial involvement unless they specify that they wish to withdraw from the study.

If a participant indicates that they wish to withdraw their consent for further participation data collected to the point of withdrawal will be retained and used. The investigator will be encouraged to ask a participant who is withdrawing which level of continued participation they agree to, if any, and to document this in the CRF. If a participant specifically requests complete withdrawal of consent, publicly available information only such as from the Birth Register may still be accessed to collect survival status. All participants will receive on-going medical care according to clinical need.

## **7. STUDY NUMBERS & POWER CALCULATION**

### **7.1 C\*STEROID Trial**

We hypothesise that corticosteroid use will reduce neonatal respiratory distress without increasing neonatal hypoglycaemia and therefore have selected co-primary outcomes of a superiority endpoint for benefit and non-inferiority endpoint for harm. The efficacy of corticosteroids is based on the success of both co-primary endpoints; therefore, no multiplicity adjustment is necessary.

Published literature only provides surrogate estimates for the incidence of respiratory distress requiring  $\geq 60$  minutes of support which varies by gestation and mode of birth. The rate of mask

and/or mechanical ventilation use is 4.4% (21/475) after planned CS  $\geq 37^{+0}$  weeks but 16.3% (258/1580) for all births at  $34^{+0}$  to  $36^{+6}$  weeks. To best estimate the incidence of this outcome we have used ADHB 2018 data for planned CS at  $35^{+0}$  to  $39^{+6}$  weeks; from a total of 1259 planned CS, 63 infants required  $>60$  minutes respiratory support (5.0%).

Using a conservative relative risk reduction of 0.5 and 5.0% event rate, **a sample size of 2424 infants (1212 per group) will have 90% power, with  $\alpha$  0.05, to detect a reduction from 5.0% to 2.5%. We will recruit 2548 infants (1274 per group) to allow for 3% drop out and design effect 1.02** (clustering of babies within mothers estimated 1.02 babies per mother with ICC of 0.8, based on the incidence of multiples at this gestation in the ADHB dataset).

There are no reliable data on rates of hypoglycaemia after planned CS  $\geq 35$  weeks in any published trials or cohort studies. Using New Zealand specific data for those within our cohort who are preterm, small- or large-for- gestational age (rates of hypoglycaemia 53%, 39% and 56% respectively) and for appropriately grown term babies (20% background rate of hypoglycaemia) and ADHB 2018 data for the proportion of babies born after planned CS at  $35^{+0}$  to  $39^{+6}$  weeks who fell into each of these four groups, we estimate an overall rate of hypoglycaemia of 28.2% (355/1259). To demonstrate the non-inferiority of corticosteroid use we have set a 10% non-inferiority margin (clinically relevant difference). **With an event rate of 28%, a sample size of 728 infants (364 per group) will have 90% power, with  $\alpha$  0.05, to reject inferiority (up to 38% hypoglycaemia in corticosteroid group), allowing for 3% drop out and design effect 1.02.**

As planned *a priori*, we have remained blinded to outcome data by treatment group for the C\*STEROID Feasibility Study allowing data to contribute to the main C\*STEROID Trial. Data from 88 mothers and 92 babies in the feasibility Study will contribute to the C\*STEROID Trial.

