These systematic reviews suggest benefit, at least in the short term. However, for all trials specific to planned CS, the risk of bias was moderate and the GRADE quality of evidence was low indicating that the true effect of corticosteroids may be substantially different than the estimate of effect given. Furthermore, recent commentaries and reviews highlight the potential for harm, supported by an unanticipated finding of the Antenatal Betamethasone for Women at Risk for Late Preterm Delivery (ALPS) trial. This is the largest trial to date, including 2827 women at high risk of imminent birth at 34+0-36+6 weeks, and although respiratory morbidity was significantly reduced, the rates of neonatal hypoglycaemia were significantly higher in babies exposed to corticosteroids (22.8% vs 14.2%, RR 1.6 95% CI 1.4-1.9). Blood glucose was not

systematically measured in all babies in the ALPS trial and only recorded as an outcome in babies requiring NNU admission; thus, it is possible that this outcome is confounded. Nevertheless, it is physiologically plausible that maternal corticosteroid use may cause neonatal hypoglycaemia.

Neonatal hypoglycaemia has been associated with a variety of brain abnormalities seen on ultrasound and MRI, and recent but accumulating evidence suggests that even transient and treated neonatal hypoglycaemia is associated with adverse childhood outcomes. A 2019 systematic review has identified nine cohort studies exploring the later effects of hypoglycaemia in children who were born 'at-risk'. Although the quality of these studies was deemed low, significant effects on early childhood visual-motor and executive function and mid-childhood neurodevelopment, literacy and numeracy are evident, making the finding in the ALPS trial a major concern which requires further consideration and evaluation.

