### **3. TRIAL HYPOTHESIS & AIMS**

#### **3.1 Hypothesis**

The maternal administration of betamethasone compared to placebo prior to planned CS at 35+0 to 39+6 weeks gestation will reduce the risk of neonatal respiratory distress without increasing the risk of neonatal hypoglycaemia.

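### At the planned size, the hypoglycaemia co-primary can be met by a result that is significantly worse on steroid, and the stated success rule would then support a claim of no increase

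*Protocol*

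**What the plan says.** Section 3.1 hypothesises that betamethasone reduces respiratory distress "without increasing the risk of neonatal hypoglycaemia". Sections 7.1 and 15.1 make this a pair of co-primary outcomes, superiority for respiratory distress and non-inferiority for hypoglycaemia, and both must succeed.

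On the margin, section 7.1 says: "To demonstrate the non-inferiority of corticosteroid use we have set a 10% non-inferiority margin (clinically relevant difference". For the placebo rate, "we estimate an overall rate of hypoglycaemia of 28.2% (355/1259". From these, "a sample size of 728 infants (364 per group) will have 90% power" "to reject inferiority (up to 38% hypoglycaemia in corticosteroid group), allowing for 3% drop out and design effect 1.02". The respiratory outcome sets the actual size: "We will recruit 2548 infants (1274 per group) to allow for 3% drop out" and a design effect of 1.02.

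Section 16 declares non-inferiority when the upper 90% confidence limit for the difference in proportions, steroid minus placebo, does not exceed 10%. It also sets two-sided 5% significance and 95% intervals for reporting. It does not say what is concluded if both criteria are met in opposite directions.

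The background (section 2.1) reports one steroid-associated increase in hypoglycaemia, from the large late-preterm trial: "the rates of neonatal hypoglycaemia were significantly higher in babies exposed to corticosteroids (22.8% vs 14.2%, RR 1.6 95% CI 1.4-1.9". After describing evidence on childhood outcomes, it adds "making the finding in the ALPS trial a major concern which requires further consideration and evaluation".

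**The concern.** The reported increase is 22.8 − 14.2 = 8.6 points, which is smaller than the 10-point margin. The protocol calls that increase a major concern but does not explain why a larger one defines acceptable harm. The only rationale is the label attached to the margin.

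The margin is then applied in a trial about 3.5 times the size that it requires (2548/728). A wide margin with narrow confidence limits leaves room for an interval that lies wholly above zero and wholly below 10 points. Such a result meets the harm co-primary. With a positive respiratory result the trial is a success by its own rule, and the hypothesis attached to that success is that hypoglycaemia is not increased. The data would show the opposite.

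**Working it through.** **Inputs.** Placebo rate 28%, margin 10 points, 90% power, 3% drop-out, design effect 1.02 and 1274 infants per group (section 7.1). One-sided 5%, from the 90% interval, and two-sided 5% for a difference (section 16).

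**The plan's own figures reproduce.** Per group, n = (1.645 + 1.282)² × 2 × 0.28 × 0.72 / 0.10² = 345.3, so 346. Inflated: 346 × 1.02 / 0.97 = 363.8, so 364 per group and 728 in total. This matches, and it confirms one-sided 5%, because one-sided 2.5% gives 424, or 446 after inflation. For the superiority outcome, 1212 × 1.02 / 0.97 = 1274.5, against 1274 stated. The effective size for hypoglycaemia is therefore about 1212 per arm.

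**Largest observed increase that is still non-inferior.** Solve d + 1.645 × SE(d) = 0.10, with SE(d) = √{[(0.28 + d)(0.72 − d) + 0.28 × 0.72] / 1212}. At d = 0.069, SE = 0.0188 and 0.069 + 0.031 = 0.100. The Farrington-Manning test gives the same limit, about 6.9 points.

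**Smallest observed increase that is significant.** Solve d = 1.96 × SE(d), where SE = 0.0186. The result is 3.65, or about 3.7 points.

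**Overlap.** Observed increases from about 3.7 to 6.9 points satisfy both criteria. Example: 33% against 28% gives a 90% interval of 1.9 to 8.1 points (non-inferior), a 95% interval of 1.3 to 8.7 points, and p = 0.008.

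**How often.** With true increase D, P(both) ≈ Φ((6.9 − D)/SE) − Φ((3.65 − D)/SE). At D = 5, SE = 1.87 points, so Φ(1.02) − Φ(−0.72) ≈ 0.61. Results from 20,000 simulated trials per row, using the Farrington-Manning test:

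| True increase (points) | Non-inferior | Significantly worse | Both |
|---|---|---|---|
| 0 | >99.9% | 2.5% | 2.5% |
| 3 | 98% | 36% | 34% |
| 4 | 94% | 57% | 52% |
| 5 | 85% | 76% | 61% |
| 6 | 69% | 89% | 58% |
| 7 | 48% | 96% | 44% |
| 8.6 | 18% | >99% | 18% |

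**Dependence on size.** At 346 effective infants per arm, non-inferiority is met up to 4.3 points and significance starts at 6.9. The two cannot coincide. The conflict arises only because the margin is carried into the larger trial.

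**Dependence on the placebo rate.** The 28% is an estimate. The same formulas at 20% (the lowest subgroup rate in section 7.1) give an overlap of 3.3 to 7.2 points and a 75% chance of both at a true +5. At 35% (my assumption) they give 3.8 to 6.8 points and 54%. The overlap persists throughout.

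**The case against.** A reader might infer that the co-primary cannot protect against the harm seen in the earlier trial. The documents do not support that. An observed increase of 8.6 points fails non-inferiority, since the limit is about 6.9, and a true increase of 8.6 points fails about 82% of the time. On the relative scale the comparison reverses: 38/28 is a relative risk of 1.36, below both the earlier trial's 1.6 and its lower limit of 1.4. Applied to 28%, even 1.4 gives 39.2%, an increase of 11.2 points and beyond the margin. The margin reaches a relative risk of 1.6 only at a placebo rate of 10/0.6 = 16.7% or less, below every subgroup rate in section 7.1.

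The benchmark is also weak. Section 2.1 says that glucose was not measured systematically in that trial and that the finding may be confounded. Its women were at 34 to 36 completed weeks. The present trial tests every baby to a schedule.

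A reader might also infer that spare sample size makes 10 points wrong, or makes 6 points right. It does neither. The 728 was derived from the margin, and a margin worked back from available power has no clinical basis.

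These points stand, and they limit what can be said about the margin itself. They do not touch the overlap, which follows from the stated rule and size without reference to the earlier trial. It can be answered that section 16 already promises 95% intervals, so an increase would be visible, and that interpretation may be left to an analysis plan not shown here. But visibility does not settle the conclusion, and the success rule and the hypothesis that it supports are fixed in the protocol.

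**Conclusion.** The point holds as a fault in the decision rule. At 28% on placebo and about 1212 effective infants per arm, every observed increase of about 3.7 to 6.9 points meets the harm co-primary while being significantly worse. For true increases of 4 to 6 points this is more likely than not (52% to 61%). The protocol would then count towards its no-increase hypothesis a result that shows an increase. The size rests on the protocol's own placebo rate, drop-out and design effect. The existence of the overlap does not depend on the exact placebo rate.

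The missing rationale for 10 points is a secondary point. The margin exceeds, on the absolute scale used for the test, the only increase that the protocol reports, and no explanation is given. That calls for a justification. It does not show that the margin is wrong.

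**What to change.** **Main change, to section 16, by amendment before unblinding.** If the two-sided 95% confidence interval for the risk difference in hypoglycaemia (steroid minus placebo) lies wholly above zero, the trial reports that hypoglycaemia was increased. It does not conclude that there was no increase, even if non-inferiority is met. Non-inferiority is to be worded as exclusion of an increase of 10 points or more. Sections 3.1, 7.1 and 15.1 should be made consistent with this.

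**Cost.** Amended wording and no extra infants. The conclusion becomes stricter: the rule overrides an otherwise non-inferior result in about 2.5% of trials with no true increase and about 34% at a true increase of 3 points.

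**Secondary, for the sponsor's clinical judgement.** Justify the 10-point margin in section 7.1 against the 8.6-point increase and its limitations, or tighten it. As information for that choice, power with no true increase is Φ(margin/1.824 − z), margin in points, where 1.824 points = √(2 × 0.28 × 0.72/1212):

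| Margin | One-sided 5% (the plan's level) | One-sided 2.5% |
|---|---|---|
| 8 points | 99.7% | 99% |
| 7 points | 98.6% | 97% |
| 6 points | 95% | 91% |

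A tighter margin would be harder to meet if there is a small true increase.

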## **8. PARTICIPANT SELECTION & RECRUITMENT**

All women booked for a planned pre-labour CS at  $35^{+0}$  to  $39^{+6}$  weeks gestation at the recruiting sites will be assessed for eligibility. Once women have been identified as eligible by meeting all of the inclusion criteria, and none of the exclusion criteria, they will be provided with information regarding the trial. This will include a parent trial summary flyer; email or telephone introduction; a participant information video; verbal information and a written participant information sheet and consent form provided by clinicians and/or site trial investigators and research staff. All women will be given time for full consideration and consultation as required. Contact telephone numbers will be provided. Clinical and/or research staff will make contact with the potential recruit and if women wish to join the study the informed consent process will be completed and written, informed consent will be obtained.

For women who decline to take part in the C\*STEROID Trial antenatal care will continue to the same standard as for all women undergoing planned CS at  $35^{+0}$  to  $39^{+6}$  weeks gestation. It will be recommended to clinicians that corticosteroids should not be available as part of this standard of care.

## **9. RANDOMISATION**

Eligible women who have provided written, informed consent to participate will be enrolled by clinicians and research staff using a web-based randomisation service operating at the Clinical Data Research Hub Research Hub (CDRH) hosted by the Liggins Institute, The University of Auckland.

Randomisation will be stratified for;

1. Gestational age at planned caesarean section 35+0-36+6, 37+0-38+6, 39+0-39+9 weeks
2. Recruiting site
3. Singleton or twin pregnancy

Women will be randomised in a 1:1 ratio to betamethasone:placebo.

The randomisation process will assign each participant with a unique study ID number. This study ID number will be required when allocating study drug treatment pack and for recording data on the CRF. The randomisation service provides 24 hour access, 7 days per week. If a woman is found not to be eligible for the trial when her details are entered into the randomisation program the program will return a screen failure notification.

## **10. TREATMENT GROUPS & STUDY DRUG**

### **10.1 Treatment Groups**

Women will be randomised to one of two groups:

1. *Corticosteroid Group*

Two doses of 11.4 mg betamethasone (Celestone Chronodose) by intramuscular injection 24 hours (+/- 4 hours) apart given within seven days of planned CS.

OR

2. *Placebo Group*

Two doses of visually matching placebo by intramuscular injection 24 hours (+/- 4 hours) apart given within seven days of planned CS.

Participants, medical professionals caring for women and trial investigators will remain blinded to treatment allocation until the trial is completed.

### **10.2 Drug Supply and Storage**

Betamethasone and visually matching placebo injections (containing no betamethasone) will be prepared by Baxter Healthcare and packaged in identical sterile syringes, for which drug stability has been confirmed by independent laboratory testing. Syringes will be labelled as C\*STEROID trial drug by staff not involved in participant recruitment and drug administration. Two syringes per allocation will be packaged into sealed treatment packs with an allocated treatment pack

number. Drugs will be stored at each recruiting site according to local hospital pharmacy procedure and under appropriate conditions (<25°C, ampoules protected from light). The Investigator at each site is responsible for study drug inventory and accountability throughout the trial.

### **10.3 Drug Administration and Assessment of Compliance**

The study drug will be administered by intramuscular injection, to the thigh, arm or buttock, by appropriately qualified clinical or research staff at the study site within seven days prior to planned CS. Two doses of study drug should be administered 24 hours apart +/- 4 hours (i.e. 20-28 hours). If the date/time of the participant's CS is brought forward and/or labour commences spontaneously before the second dose has been administered it should still be given as long as it is ≥20 hours following the first dose. If birth is planned (CS) or inevitable (spontaneous labour) and it is <20 hours since the first dose the second dose should not be given. There is no minimum timeframe between the second dose and the planned CS (or expected birth). The timing of each dose and compliance will be recorded on the CRF.

### **10.4 Emergency Unblinding**

In the event that there is an immediate need for the treating doctor to know a participant's treatment allocation to ensure patient safety it will be possible to break the randomisation code. The facility to perform emergency unblinding will be available 24 hours per day. Participant unblinding can be completed by contacting the Auckland coordinating centre (contact details page one).

## **11. TREATMENT DURATION/INDICATIONS TO STOP TREATMENT**

### **11.1 Treatment Duration**

Randomised participants will be given the first dose of study drug within seven days of their planned CS and a second dose 24 hours (+/- 4 hours) later. The first dose of study drug should be scheduled to allow for the administration of two doses 24 hours (+/- 4 hours) apart prior to the participants planned CS. No further doses of study drug or antenatal corticosteroids will be given, even in the event of a delayed planned CS date.

### **11.2 Indications to Stop Treatment**

1. Significant maternal reaction to the first injection as determined by the clinician.
2. Birth required on clinical grounds prior to scheduled second dose of study drug.
3. Maternal request.

## **12. DATA COLLECTION**

### **12.1 Participant Schedule**

The study procedures for randomised participants are summarised in the flow chart below.

#### **Individual Participant Trial Flow Chart**

### **12.1.1 Baseline Data Collection**

Data will be collected on current and past medical history and demographics including date of birth, ethnicity, height and weight, past obstetric history, past medical history, complications to date in current pregnancy, medication use in pregnancy, indication(s) for CS and indication for timing of CS.

### **12.1.2 Baseline Questionnaires**

All participants will complete the following questionnaires at the first study visit:

- The SF-36 quality of life questionnaire to assess overall health and wellbeing.
- The Edinburgh Postnatal Depression Scale (EPDS) to assess mental wellbeing.

The EPDS will be reviewed by the local site once questionnaires are completed. Where the overall EPDS score  $\geq 13$  or item 10 is marked as yes, appropriate follow up will be made by the local site investigator or research midwife/coordinator.

### **12.1.3 Randomisation and Study Drug Allocation**

The randomisation process will assign each participant with a study drug treatment pack number. The system will only allocate treatment packs assigned to and available at the individual recruiting site. Each treatment pack contains two syringes containing 11.4 mg betamethasone or visually matching placebo. The second dose syringe will be kept securely at the recruiting site prior to second dose.

### **12.1.4 Study Drug Treatment**

First and second doses of study drug will be administered by clinical and qualified research staff within seven days of planned CS and 24 hours (+/- 4 hours) apart. Timing and compliance will be recorded in the CRF.

At the time of the first dose women will be provided with a Clinical Trial Participant Alert Card which will include space to record any adverse effects. At the second dose visit and on admission for planned CS, the Participant Alert Card will be reviewed and women will be asked to report any adverse reactions (local or systemic). These will be recorded in the CRF.

### **12.1.5 Consent for the child/children**

Written confirmation of consent for the child/children to be part of the research will be obtained for New Zealand participants as soon as possible after birth has occurred, this is required pursuant to section 36 of the Care of Children Act (NZ). In circumstances where the mother is unable to provide consent other parent or guardian consent should be obtained. If this consent is delayed neonatal blood glucose monitoring must be performed for safety reasons and consent should be sought as soon as this is appropriate.

